3.2.2. Study Timelines

Study timelines are mapped out for the two trials and for OPERA in [Table 1](#).

TMB-202

- Recruitment: 2008-2010
- Follow-up: through week 24
- Index: date of first IBA infusion

TMB-301/311

- Recruitment: 2015-2018
- Follow-up: through week 96
- Index: date of first IBA infusion

⁴ CAB had not yet been approved at the time and is not indicating for ART-experienced PWH who are failing their current regimen

OPERA

- Identification of study participants: 01JAN2008 to 31DEC2020
- Censoring criteria:
 - Initiation of any of the following ARVs:
 - INSTI
 - PI
 - Fusion inhibitor (FI)
 - Gp120 inhibitor
 - IBA
 - Doravirine
 - Blinded ARV
 - >45 days without ART
 - 12 months after last clinical contact (i.e., telephone contact, visit, lab test, or consultation)
 - Death
 - Study end (i.e., extract date; TBD)
- Index: date of regimen initiation

Table 1. Alignment of study timelines for the clinical trials and OPERA

	Week -1	Index	Week 1	Week 24	Week 48	Week 60	Week 96
TMB-202	Failing Regimen	IBA 2000mg every 4 weeks + OBR ^a					
		IBA 800mg every 2 weeks + OBR ^a					
TMB-301/311	Failing Regimen	IBA 2000mg + Failing Regimen		IBA 800mg every 2 weeks + OBR ^a			
OPERA	Failing Regimen	Index regimen ^b					

^a Changes in OBR were allowed during follow-up

^b Some changes in ARVs will be allowed to be consistent with trial designs; person-time will be censored at initiation of an INSTI, PI, fusion inhibitor, Gp120 inhibitor, IBA, doravirine or a blinded ARV

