It is important to assess the comparative effectiveness of IBA compared to other regimens used in the routine clinical care of HTE PWH with MDR HIV. The use of external controls can provide valuable information and context to interpret the results of clinical trials when randomization to a control arm cannot be performed.^[17] Using comparable populations and larger sample sizes may reduce bias and improve the power of analyses. The OPERA (Observational Pharmaco-Epidemiology Research & Analysis) cohort, a large US electronic health record (EHR) database, is well suited for this as the OPERA and trials populations arose from the same geographic location (i.e., US), and the number of OPERA PWH potentially meeting inclusion criteria is high. Therefore, an external comparison of IBA+OBR from trials to non-IBA OBR in routine clinical care in the OPERA cohort may confirm results from prior studies suggesting viral control benefits of IBA+OBR.

Study Objectives

Primary Objective:

To assess the virologic effectiveness of 800 mg IBA every 2 weeks + OBR (TMB-202 & TMB-301/311 trials), compared to non-IBA OBR in routine clinical care (OPERA cohort), among HTE PWH.

Sensitivity Objective 1:

To assess the robustness of results from the primary objective to the viremia threshold for inclusion in the OPERA non-IBA OBR group (main: VL >1,000 copies/mL vs. sensitivity: VL >200 copies/mL).

Sensitivity Objective 2:

To replicate previous analyses of the European registry as closely as possible, taking into consideration the differences between the registry and OPERA datasets

Data sources

Data from the phase 2 clinical trial TMB-202, as well as the phase 3 trial TMB-301 and its extension TMB-311 will be used for the treatment arm of the study (IBA+OBR). The OPERA cohort, which includes complete EHR data from over 143,000 PWH across 142 separate locations throughout the US, will be used for the control arm (non-IBA OBR).

Study Design

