All TMB-202 and TMB-301/311 trial participants randomized to 800 mg IBA every 2 weeks with or without a loading dose will be included in the main analyses. From the OPERA cohort, adult PWH with resistance from three ARV classes will be considered for inclusion (see section 3.2.1 for more details). OPERA PWH initiating a new non-IBA OBR between 01JAN2008 and 31DEC2020 will be included; person-time will be censored at the first of (a) initiation of a select potent ARV, (b) >45 days without ART, (c) 12 months after last clinical contact, (d) death, or (e) study end (i.e., extract date of the dataset; TBD). Viral suppression (i.e., <200 copies/mL) and undetectable viral load (i.e., <50 copies/ml) will be assessed at each of the timepoints of interest (i.e., weeks 24, 48, 60 and 96), using the closest measurement to the timepoint within a ± 6 -week window.

Statistical Analyses

Multiple imputation will be used to ensure that eligible OPERA participants can contribute to all timepoint analyses even if their routine clinical care resulted in viral loads being measured outside of the ranges defined in the protocol. To prevent the introduction of a bias towards the null, imputation will be performed in the OPERA non-IBA OBR group separately.^[18] 95% confidence intervals will be obtained through bootstrapping.

First, the data will be sampled with replacement to create 500 bootstrap samples. Within each bootstrap sample, multiple imputation will be implemented using chained equations, producing 10 imputed datasets per bootstrap sample.

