3.3.2. Outcome Definition

Virologic outcomes:

- Viral suppression (<200 copies/mL)
- Undetectable VL (<50 copies/mL)

Timepoints of interest:

Weeks 24, 48, 60, 96 after index (closest measurement within a ± 6 -week window)

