4.4. Primary Objective: External Comparison of Virologic Effectiveness

The comparative virologic effectiveness of IBA+OBR vs. non-IBA OBR will be assessed at each timepoint for both viral suppression (VL < 200 copies/ml) and undetectability (VL < 50

copies/ml). Within each imputed dataset, estimates of risk will be derived from SMR-weighted Kaplan-Meier curves. The cumulative probability of viral suppression or undetectability will be estimated at each timepoint of interest for each arm, from which risk ratios will be calculated.

The distribution of estimates from all 5,000 datasets will be used to obtain the final estimate (mean) and 95% confidence intervals (2.5th and 97.5th percentiles).

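### Controls are censored after more than 45 days without ART, with no stated trial-arm rule; this probably overstates control suppression, and the direction of the risk ratio bias is open

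*Combined protocol and SAP*

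**What the plan says.** The opening summary, under Study Design, says of the OPERA group that "person-time will be censored at the first of (a) initiation of a select potent ARV, (b) >45 days without ART", followed by time since last contact, death and study end. Section 3.2.2 repeats the list under OPERA, including ">45 days without ART". For the trials, the same section gives only recruitment years, the index date and an end of follow-up: for TMB-202, "Follow-up: through week 24", and for TMB-301/311, week 96. It gives no rule for a trial participant who stops IBA, stops the background regimen or drops out.

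Section 3.3.2 defines the outcomes at weeks 24, 48, 60 and 96 from the "closest measurement within a ± 6 -week window". In Section 4.4, "estimates of risk will be derived from SMR-weighted Kaplan-Meier curves", and the RR at a given week is the ratio of the two arms' curve values. The weights in Section 4.3 use baseline covariates only. No censoring weights or competing-event method are planned. Section 4.2 imputes missing OPERA viral loads but does not say whether this extends past the censoring date. The limitations in Section 6.1 do not mention informative censoring, and no estimand is stated for treatment interruption.

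**The concern.** Kaplan-Meier is valid if people censored at a given time have the same later chance of the event as those still under observation. Controls enter with a viral load above 200 copies/mL and resistance in three classes (Section 3.2.1). Someone in that group who has taken no ART for over six weeks is unlikely to have the same prospects as someone still on a regimen.

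The stated interest is the "comparative effectiveness of IBA compared to other regimens used in the routine clinical care of HTE PWH with MDR HIV". In routine care, stopping is part of how a regimen performs. Censoring at the gap moves the control estimate towards suppression among people who stay on ART. The trial figure beside it may or may not be built the same way, because the plan does not say, so a reader could not tell whether the two risks in the ratio answer the same question.

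**Working it through.** The plan gives no suppression rate, gap rate or effect size, so it has no figure to reproduce. All rates below are assumptions.

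**Inputs from the plan.** The treated group is 59 + 40 = 99, and there are about 200 controls (Section 5). In TMB-301/311, 27 of 40 participants entered the extension, with four deaths before and two during it (Section 3.1.2). At most 27 of the 99 therefore have planned follow-up past week 24.

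**Step 1: overstatement of control risk, first-event curve.** Let h be the hazard of suppression on ART and g the hazard of an ART gap, both constant over one interval. Assume nobody is suppressed after a gap.
- Gaps censored: 1 − exp(−h).
- Gaps counted as not suppressed: h/(h+g) × [1 − exp(−(h+g))].

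With on-ART risk 0.50, h = −ln(0.50) = 0.693. Gap probabilities of 5%, 10% and 20% give 0.489, 0.477 and 0.454 in place of 0.50, an overstatement by factors of 1.02, 1.05 and 1.10. Across on-ART risks of 0.30 to 0.70 and gap probabilities of 2% to 20%, the factor runs from 1.01 to 1.11.

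**Step 2: effect on the RR if trial stoppers are not censored.** Take treated risk 0.60 and control Kaplan-Meier risk 0.55, so the planned RR is 0.60/0.55 = 1.09. Here h = −ln(0.45) = 0.799.

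| Gap probability | Control risk, gaps as failures | RR, gaps as failures | Planned RR divided by that RR |
|---|---|---|---|
| 5% | 0.538 | 1.12 | 0.98 |
| 10% | 0.526 | 1.14 | 0.96 |
| 20% | 0.500 | 1.20 | 0.91 |

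For 10%, g = 0.105 and 0.799/0.904 × (1 − 0.45 × 0.90) = 0.526.

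**Step 3: status at the timepoint instead.** Sections 3.3.2 and 4.4 leave open whether the curve counts first suppression or status at the timepoint. If status is used and every stopper is dropped from the control denominator, with none suppressed, control risk with stoppers restored is (1−q) × 0.55. At q = 5%, 10% and 20% that is 0.523, 0.495 and 0.440, giving RRs of 1.15, 1.21 and 1.36. The planned RR is then 0.95, 0.90 or 0.80 of those values. If 10% of stoppers are suppressed anyway, the factors are about 0.96, 0.92 and 0.84. These are upper bounds on the distortion, since Kaplan-Meier keeps a stopper's person-time and events before the gap.

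**Step 4: trial stoppers censored as well.** Take on-treatment risks of 0.40 (control) and 0.50 (trial), so the RR with both arms censored is 1.25.
- Control gaps 10%, trial dropout 10%: RR with both counted as failures is 1.252, factor about 1.00.
- Control gaps 10%, trial dropout 20%: RR is 1.190, factor 1.05, in favour of IBA.
- Over control gaps of 5% to 20% and trial dropout of 0% to 20%: factor 0.91 to 1.08.

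**Step 5: restarting ART.** With control risk 0.40 and 10% gaps, the overstatement falls from 1.05 if nobody is suppressed after a gap, to 1.02 if the later hazard is half the on-ART hazard, to 1.00 if it is equal.

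**The case against.** A reader might infer that the RR is simply biased against IBA. The documents do not support that. They are silent on trial participants who stop, and silence is not a rule that keeps them in. Section 4.4 applies Kaplan-Meier to each arm, so trial dropouts may be censored on the same assumption, and Step 4 shows that the bias can then vanish or change sign.

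A reader might also infer an overstatement of 1/(1−q). That describes deleting stoppers outright. Under a first-event curve the effect is roughly half as large, and a gap after first suppression has no effect.

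Three further points carry weight. An on-ART target is legitimate if it is stated and its censoring assumption is addressed, so the case for replacing the primary analysis is not made. Section 6.1 warns that record-keeping varies and that patients may attend several practices, so some apparent gaps are record gaps; counting all of them as failures would lower control suppression and favour IBA. Imputation might also bring post-gap timepoints back in. But Section 4.2 does not say so, and the imputation covariates in Section 3.3.3 include the index regimen but no indicator of being off ART.

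None of this removes the core point: the censoring is probably informative, and it is specified for one arm only.

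**Conclusion.** The concern holds in limited form. Censoring controls at an ART gap tends to overstate control suppression relative to an analysis that counts people off ART as not suppressed. The overstatement is about 2%, 5% or 10% for gap probabilities of 5%, 10% or 20%, assuming constant hazards, a first-event curve, an on-ART risk of 0.50 and no suppression after a gap. If trial stoppers are fully followed or counted as failures, the RR is too low by the factors in Step 2, or at most those in Step 3. If they are censored, the direction is undetermined. Among about 200 controls a 10% gap rate would be some 20 people, but the documents give no rate. This should be settled in the plan before the analysis is run. It is also one item in a wider question about the OPERA-only censoring list.

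**What to change.** In the opening summary and Section 3.2.2, state one ART-gap rule that applies to both arms, including how trial participants who stop all ART are handled. State the target of estimation for interruptions, and say in Section 4.2 whether viral loads after censoring are imputed.

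Add a prespecified analysis in both arms that keeps people with a gap in the denominator. Count them as neither suppressed nor undetectable at timepoints while they remain off ART, but use any viral load observed in the window where there is one. This respects suppression observed after a restart. Report it beside the censored analysis, or beside one with inverse-probability-of-censoring weights, and tabulate the number censored by reason and arm.

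The cost is SAP wording and a little programming. OPERA ART dates are already needed for the existing rule; the trial data must supply stop dates, which the documents do not describe. The drawback is that some EHR gaps may not be true stops, which is why both versions should be shown.

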Within each imputed dataset, logistic regression will be used to obtain the PS and will include baseline values for important predictors of regimen selection. Continuous variables will be modeled flexibly with either quadratic terms or restricted cubic splines. Candidate covariates for the PS model include age, sex, VL, CD4 cell count, index date, agents in the OBR, resistance to ARVs, and the number of potent ARV in the OBR scaled by level of resistance. SMR weights are set to 1 in the treated population (i.e., IBA+OBR in TMB trials). In the control population (i.e., non-IBA OBR in OPERA), SMR weights are calculated as $PS/(1-PS)$.^[20] The final set of variables included in the PS model will be determined by the distribution of weights, as well as the balance of covariates across groups.

The distribution of weights will be evaluated for the presence of large weights. Model specification will be adjusted to obtain a mean weight as close to 1 as possible and avoid extreme weights. Weight trimming may be considered to reduce the impact of extreme weights.^[42] In such case, trimming would be performed at the 1st and 99th percentile: all weights with a value below the 1st percentile (above the 99th percentile) would be set to the value of the first percentile (99th percentile).^[42] The extent of trimming will be assessed based on the distribution of weights and adjusted as needed. The balance of covariates included in the PS model across groups will be assessed using standardized differences estimated before and after applying the SMR weights. A threshold of <10% will indicate an acceptable balance.^[43]

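### OPERA controls are censored when a listed potent ARV is started, while trial participants stay in follow-up through OBR changes, so the risk ratio compares two estimands and control censoring is plausibly informative

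*Combined protocol and SAP*

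**What the plan says.** Two footnotes to Table 1 (section 3.2.2) set the rules. Footnote a covers the trial OBR: "Changes in OBR were allowed during follow-up". No section lists a censoring rule for the trial arm when the OBR changes. Trial follow-up is described only by its length: "Follow-up: through week 24" for TMB-202 and "Follow-up: through week 96" for TMB-301/311.

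Footnote b covers OPERA. It opens with "Some changes in ARVs will be allowed to be consistent with trial designs" and continues: "person-time will be censored at initiation of an INSTI, PI, fusion inhibitor, Gp120 inhibitor, IBA, doravirine or a blinded ARV". The synopsis (Study Design) has the same rule, attached to OPERA only: "person-time will be censored at the first of (a) initiation of a select potent ARV".

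Section 4.4 then states that "estimates of risk will be derived from SMR-weighted Kaplan-Meier curves", with risk ratios taken at weeks 24, 48, 60 and 96. The propensity model behind the weights (section 4.3) "will include baseline values for important predictors of regimen selection".

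**The concern.** The trial arm is analysed whatever happens to the background regimen. The control arm is analysed only until a listed potent agent is started. The first is close to a treatment-policy estimand. The second is a while-on-regimen or hypothetical one. A ratio of the two has no single interpretation, and the plan does not say which is intended.

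The control rule also strains the estimator. Kaplan-Meier needs people censored at a given time to have the same later chance of suppression as those still unsuppressed and in follow-up, given the weights. Section 4.5.1 says that in routine care regimens are often changed before viral load climbs above 1,000 copies/mL. That remark concerns the entry threshold, but it shows that the plan expects viral load to influence regimen change. Viral load is also the outcome (section 3.3.2). If controls who respond poorly are the ones who start a listed agent, the assumption fails.

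The mismatch sits in the primary comparison and is not mentioned among the limitations in section 6.1.

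**Working it through.** **1. The rules side by side**

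| Event after index | Trial arm | OPERA arm |
|---|---|---|
| Background change outside the list | Stays in | Stays in (footnote b) |
| Start of a listed agent other than IBA | No censoring stated (footnote a) | Censored (footnote b) |
| Start of IBA | Not applicable | Censored |

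The arms differ in the second row only. The plan does not say how many trial participants started a listed agent, or which changes the trials permitted.

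**2. Does anything in the plan correct for it?**

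- Weights: baseline covariates only (section 4.3). There are no censoring weights.
- Sensitivity analyses: section 4.5.1 varies the viral load threshold. Section 4.5.2 uses propensity score matching and complete cases. Neither varies the censoring rule.
- Imputation: section 4.2 does not say whether viral loads after censoring are imputed. Section 3.3.3 lists a person's own interim viral loads, their timing and CD4 counts as candidate predictors.

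**3. Can it matter?**

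The plan gives no event or switching rates, so there is no figure to reproduce. As an illustration, both arms were simulated with no true difference (400,000 per arm, weekly steps, unweighted Kaplan-Meier to first suppression). One arm was followed through listed-agent starts and the other was censored at them. Every rate below is an assumption.

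- Half of each arm are responders (weekly suppression hazard 0.04) and half are not (0.003).
- Only non-responders start a listed agent, from week 4, at 10%, 25% or 50% per 24 weeks. The weekly hazard is −ln(1−x)/24, which gives 0.0044, 0.0120 and 0.0289.
- Weekly suppression hazard after the start: 0.005, 0.02 or 0.05.

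Check of the no-switch risk: 0.5(1−0.96^24) + 0.5(1−0.997^24) = 0.347 at week 24. The same formula with 96 gives 0.615 at week 96. The simulation printed about 0.347 and 0.615.

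Results at week 96:

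| Switching per 24 weeks | Controls censored | Censored curve ÷ no-switch risk | Ratio of arms at post-change hazard 0.005 / 0.02 / 0.05 |
|---|---|---|---|
| 10% | 15% | 1.04 | 0.98 / 1.06 / 1.12 |
| 25% | 30% | 1.11–1.12 | 0.93 / 1.10 / 1.20 |
| 50% | 43% | 1.32 | 0.81 / 1.04 / 1.15 |

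The true ratio is 1.00 in every cell. At week 24 the censored curve was 1.01 to 1.11 times the no-switch risk, and the ratio of arms ran from 0.92 to 1.13.

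In a second scenario, any still-viremic person could switch from week 12, whatever their prognosis (no-switch risk about 0.47 at week 24 and 0.63 at week 96). The censored curve then matched the no-switch risk, so censoring was not informative. The ratio still ran from 1.00 to 1.08 at week 24 and from 1.02 to 1.49 at week 96, because only one arm was credited with suppression after a change.

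The two mechanisms are separate. Informative censoring pushes the ratio down, and one-sided credit for later suppression pushes it up.

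**The case against.** The best defence is that alignment was considered. Footnote b allows some control changes expressly to match the trials, and the real mismatch depends on trial records that are not in the documents. If few trial participants started a listed agent, one-sided credit is small. TMB-202 supplies 59 of the 99 treated participants and stops at week 24, which leaves little time for suppression after a change to accrue. All of this stands as a limit on size. It does not remove informative censoring of controls, which needs no trial OBR change at all. After week 24 the trial curve rests on TMB-301/311, where follow-up is long enough for changes to matter.

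Four stronger readings are tempting but unsupported.

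- A reader might infer that censored controls are treated like people doing well. In a curve of time to first suppression, those already suppressed have left the risk set. A control censored while viremic takes the hazard of controls still viremic, so the distortion is weaker.
- A reader might size the bias by mixing a success proportion among uncensored controls with a lower one among the censored. That is a complete-case proportion, not the planned Kaplan-Meier estimate, and it moves the ratio in one direction only.
- A reader might infer that failing controls would be imputed from successful ones. Section 3.3.3 allows a person's own interim viral loads as predictors. What is missing is a statement about values after censoring.
- A reader might infer that trial participants could start any listed agent and stay in follow-up. Footnote a does not list the permitted changes.

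**Conclusion.** The point holds for the listed potent agents. Followed as written, the plan compares a trial arm analysed through background changes with a control arm censored at a listed-agent start. Nothing in the weighting, the estimator or the sensitivity analyses addresses the difference.

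That control censoring is informative is an inference from section 4.5.1, not a stated fact. Some changes will be made for tolerability or drug interactions, factors that section 1 names among the reasons for lost treatment options.

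The documents fix neither the size nor the direction of the net bias, and they do not support a claim that the plan favours IBA or disfavours it. The simulated ranges show only that a null effect could look like benefit or harm under assumed rates. They assume that the curve runs to first suppression and that both arms are followed to week 96. They are not estimates for this study. The matter should be settled before the analysis is run.

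**What to change.** In section 4.4, state the estimand for regimen change. Then add to sections 4.4–4.5:

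1. An analysis that keeps OPERA controls in follow-up through later ARV changes other than starting IBA, so that both arms are analysed regardless of background changes. This needs OPERA data only.
2. Where trial OBR change dates are available, analyses that apply the same listed-agent rule to both arms. Run one as censoring, with inverse-probability-of-censoring weights from time-updated viral load and CD4 where the data allow. Run the other counting the change as not suppressed.

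In section 4.2, state that viral loads after censoring are not imputed in the censored analysis. Report the number and timing of listed-agent starts by arm, so that readers can judge whether the issue is material.

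The cost is SAP wording and extra runs. Analysis 1 makes the comparator a treatment strategy rather than a fixed regimen, and it may admit after index agents that section 3.2.1 excludes from the index regimen. Both versions of analysis 2 need trial OBR change dates. One rule for both arms removes the asymmetry but does not by itself make censoring non-informative, which is why the time-updated weights are needed.
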